Study Protocol

Title: A Multicenter, Randomized Controlled Trial Comparing Retrograde Intrarenal Surgery (RIRS) Using Tip-Flexible Suction Access Sheath with Standard Percutaneous Nephrolithotomy (PCNL) for the Treatment of 2-3 cm Unilateral Renal Stones

NCT Number: NCT00000000 (To be updated after registration approval)

Document Date: May 15, 2025

Study Protocol (Version X2.0 / April 8, 2025)

Title:

A Multicenter, Randomized Controlled Trial Comparing Retrograde Intrarenal Surgery (RIRS) Using Tip-Flexible Suction Ureteral Access Sheath (TFS-UAS) with Standard Percutaneous Nephrolithotomy (PCNL) for the Treatment of 2-3 cm Unilateral Renal Stones

Protocol ID: 20250408 Sponsor: Changhai Hospital Principal Investigator: [name] Participating Centers:

- Department of Urology, Xinhua Hospital, Shanghai Jiao Tong University School of Medicine
- Department of Urology, Zhejiang Provincial People's Hospital
- Department of Urology, The First Hospital of Jiaxing
- Department of Urology, The 902nd Hospital of PLA Joint Logistics Support Force

Study Period: April 2025 - June 2026

1. Background

Ureteroscopy (RIRS), percutaneous nephrolithotomy (PCNL), and extracorporeal shock wave lithotripsy are standard minimally invasive treatments for renal stones. In recent years, the use of RIRS has increased due to its flexibility, reduced trauma, and repeatability. To further improve outcomes, a new tip-flexible suction ureteral access sheath (TFS-UAS) has been developed. This sheath has a soft, bendable tip (~10 cm) and integrates continuous suction to reduce intrarenal pressure, enhance stone clearance, and improve visualization.

While both RIRS and PCNL are recommended for renal stones of 2-3 cm in diameter, there is limited prospective comparative evidence between TFS-UAS-assisted RIRS and standard PCNL. This study addresses this gap.

2. Objectives

To compare the clinical efficacy and safety of tip-flexible suction sheath-assisted RIRS and standard PCNL in the management of 2-3 cm unilateral renal stones.

3. Study Design

A prospective, multicenter, randomized controlled trial.

Population: Adults aged 18-80 with unilateral renal stones measuring 2-3 cm, eligible for surgical intervention.

Sample Size Calculation: Assuming 85% SFR for RIRS and 95% for PCNL, with alpha=0.05 and power=0.80, the minimum sample size per group is 140. Allowing for 10% dropout, each group will include at least 154 patients; total n=308.

Randomization: Block randomization will be used to allocate patients into either the RIRS group or PCNL group.

Blinding: Open-label.

4. Eligibility Criteria

Inclusion Criteria

- 1. Age 18-80 years
- 2. ASA physical status I-III
- 3. CT-confirmed unilateral renal stones measuring 2-3 cm
- 4. Signed informed consent

Exclusion Criteria

- 1. Anatomical urinary tract anomalies (e.g., horseshoe kidney, ileal conduit)
- 2. Uncontrolled urinary tract infection
- 3. Absolute contraindications to RIRS or PCNL
- 4. Inability to understand or comply with study procedures

5. Interventions

RIRS Group (Experimental):

- Under general anesthesia, a semirigid ureteroscope is used to assess the ureter.
- A TFS-UAS (F10 or F12.5) is inserted into the renal pelvis under guidewire.
- Flexible ureteroscope with irrigation and suction is used.
- Holmium laser (200 um) is applied for lithotripsy.
- Stone fragments are evacuated via suction or extracted with a basket.
- A double-J stent is placed postoperatively.

PCNL Group (Control):

- Under general anesthesia, ureteral catheter is placed and patient is positioned prone.
- Percutaneous access is established under ultrasound guidance.
- Tract dilation up to F22, nephroscope introduced.
- Holmium laser (550 um) used for stone fragmentation.
- Double-J stent and nephrostomy tube placed postoperatively.

6. Outcome Measures

Primary Outcome

- Stone-Free Rate (SFR) at 3 months: defined as no residual stones or residual fragments <2 mm on non-contrast CT.

Secondary Outcomes

- Incidence of postoperative infection (SIRS criteria)
- Change in serum procalcitonin and hemoglobin levels
- Postoperative pain score (VAS)
- Hospital length of stay
- Need for secondary procedures
- Complication rate (Clavien-Dindo classification)
- Cost and stone composition analysis

7. Follow-Up

Patients will be followed up via telephone, outpatient visit, or WeChat at 3 months post-op. CT will be used to assess residual stones.

8. Statistical Analysis
SPSS will be used for data analysis.
Continuous variables: mean +/- SD, t-test or Mann-Whitney U test as appropriate.
Categorical variables: test.
Multivariate logistic regression for outcome prediction.
Multiple imputation for missing data.
p < 0.05 considered statistically significant.

9. Safety and Monitoring

Case report forms (CRFs) will be completed for each subject.

Data will be reviewed by monitors and verified by data managers.

Serious infections (e.g., temp > 40, HR > 140 bpm, PCT > 100, bacteremia) may lead to trial withdrawal for safety.

10. Ethics and Regulatory Compliance
Approved by institutional ethics committees.
Personal information will be kept confidential and stored securely.
Regulatory bodies may audit data when required.
Participants may withdraw at any time without penalty.

11. Publication Plan

Results will be submitted to peer-reviewed journals (SCI-indexed or national core journals) and presented at academic conferences.

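### Does a sample size built on RIRS clearing 10 points fewer stones leave the trial with nothing to conclude if the arms turn out similar?

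*Protocol*

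**What the plan says.** Section 3 (Sample Size Calculation) fixes the planning rates, error rates and size: "Assuming 85% SFR for RIRS and 95% for PCNL, with alpha=0.05 and power=0.80, the minimum sample size per group is 140". It does not say whether alpha is one- or two-sided, and it names no hypothesis type or margin. Section 5 labels RIRS as the experimental arm and PCNL as the control.

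The aim in section 2 is neutral: "To compare the clinical efficacy and safety of tip-flexible suction sheath-assisted RIRS and standard PCNL". The only inference rule, in section 8, is "p < 0.05 considered statistically significant".

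Section 1 gives the appeal of the technique: "the use of RIRS has increased due to its flexibility, reduced trauma, and repeatability". It says of the new sheath that it "integrates continuous suction to reduce intrarenal pressure, enhance stone clearance, and improve visualization".

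**The concern.** A new technique is usually tested in the hope that it does better, or at least not materially worse. Here the planning alternative has the new technique 10 points below the standard. The outcome for which the trial has 80% power is thus a finding against RIRS.

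Section 1 presents RIRS as the less traumatic option, so readers will ask whether any loss in SFR is small enough to accept in exchange for less infection, pain or time in hospital. A p-value above 0.05 does not answer that. Someone who took it as proof of comparable clearance could overlook a loss as large as the one the trial was sized to detect.

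**Working it through.** **Inputs (protocol, section 3).** SFR 85% (RIRS) and 95% (PCNL), a difference of 0.10 with mean 0.90; alpha 0.05; power 0.80; 140 per group before dropout.

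**Reproducing the 140.** Two-sided, pooled variance under the null:

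n = [1.960 × √(2 × 0.90 × 0.10) + 0.842 × √(0.85 × 0.15 + 0.95 × 0.05)]² / 0.10²
= [1.960 × 0.4243 + 0.842 × 0.4183]² / 0.01 = 140.1.

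The unpooled form gives 137.4. A one-sided test (1.645 in place of 1.960) gives 110.2. The stated figure is therefore a two-sided difference test, correctly computed.

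**What 140 evaluable per arm delivers.** Exact enumeration of two binomials, Pearson chi-square without continuity correction:

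| True SFR, RIRS / PCNL | Significant, RIRS lower | Significant, RIRS higher | p ≥ 0.05 |
|---|---|---|---|
| 85 / 95 | 81.4% | under 0.001% | 18.6% |
| 90 / 95 | 34.5% | 0.02% | 65.5% |
| 92 / 95 | 16.4% | 0.1% | 83.5% |
| 93 / 95 | 9.9% | 0.4% | 89.8% |
| 90 / 90 | 2.4% | 2.4% | 95.2% |
| 95 / 95 | 2.4% | 2.4% | 95.2% |
| 97 / 95 | 0.2% | 12.4% | 87.3% |
| 95 / 85 | under 0.001% | 81.4% | 18.6% |

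The figure near 95% belongs to equal rates only, where it is 1 − alpha at any sample size. The first and last rows mirror each other: the test is as sensitive to a 10-point advantage for RIRS as to a 10-point deficit.

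The name of the categorical test is missing from section 8 as extracted, so Pearson is an assumption. With Fisher's exact test the non-significant share is 72.7% at 90/95, 93.6% at 93/95, and 96.8% to 97.7% at equal rates of 90% and 95%.

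**What a non-significant result can hide.** Take 126/140 (90%) against 133/140 (95%). The pooled standard error is √[(259/280) × (21/280) × 2/140] = 0.0315, so z = −0.05 / 0.0315 = −1.59 and p = 0.11. The unpooled standard error is √[(0.90 × 0.10 + 0.95 × 0.05) / 140] = 0.0313, so the 95% confidence interval is −5.0 ± 6.1, or −11.1 to +1.1 points. Among non-significant trials the interval still reaches a 10-point deficit in 83% at 85/95, 43% at 90/95, 18% at 90/90 and 2% at 95/95. The interval shows this directly, with no change to the design.

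**Whether a margin would improve matters.** The protocol gives none, so these margins are illustrative. With a 10-point margin, the probability at 140 per arm that the lower 95% limit lies above −10 points is 80% at 90/90 and 96% at 95/95, but 3% at 85/95. At the planning rates the true difference equals that margin, so no sample size would help. A 5-point margin with 80% power needs about 299 per arm at 95/95 or 566 at 90/90. A margin thus means a different trial question with new planning rates.

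**The case for a change.** The strongest case for a change is that the sample size and the alternative behind it are fixed in the protocol and no later analysis plan can alter them. The new arm is not expected to win on SFR, so the clinically useful question is how much clearance is lost. A bare significance rule does not answer it, and the cure would cost only a few sentences: label the test, make the risk difference with its 95% interval the primary result, and say that non-significance is not similarity.

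The calculations behind this case stand, as does the warning about reading p ≥ 0.05 as comparability. The step to a needed change does not follow. The mismatch alleged is with a favourable conclusion about RIRS that the protocol nowhere promises. Looking for an important deficit in a less invasive technique is a legitimate aim for a comparative trial, and finding one would be informative. The lower assumed SFR alongside reduced trauma is an ordinary trade-off, and the sheath's enhanced clearance in section 1 can be read as an improvement to RIRS, without any claim over PCNL. The proposed sentences leave the sample size and alpha as they are. The effect measure, interval and interpretation are commonly set in the analysis plan, which may exist but was not available here.

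**Conclusion.** The concern describes the design correctly but shows no error or contradiction in it. The 140 per group is a sound two-sided difference calculation, consistent with a neutral objective and a 5% significance rule. Followed as written, the plan gives a valid comparison: about 81% power for a 10-point difference in either direction between 85% and 95%, and a non-significant result in about 95% of trials if the rates are equal, 90% at 93/95 and 65% at 90/95. These figures assume 140 evaluable patients per arm and a Pearson test.

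The unstated sidedness is a small gap that the arithmetic itself settles, since only the two-sided form gives 140. Reporting the risk difference with its 95% confidence interval, and not treating p ≥ 0.05 as similarity, is what a competent analyst would do anyway. Adopting a non-inferiority margin would be a separate and debatable design decision, and the absence of one is not a defect here. No change to the plan follows.

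### The enrolment of 154 per group absorbs about 9% dropout, not the stated 10%, and so falls just short of the protocol's own minimum of 140

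*Protocol*

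**What the plan says.** The protocol's Section 3 gives the whole calculation in two sentences. The assumptions are "Assuming 85% SFR for RIRS and 95% for PCNL", "with alpha=0.05 and power=0.80", from which "the minimum sample size per group is 140". The allowance for loss follows: "Allowing for 10% dropout, each group will include at least 154 patients; total n=308". The inflation formula is not shown. The only other text that bears on incomplete follow-up is one line in Section 8 (Statistical Analysis): "Multiple imputation for missing data".

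**The concern.** The minimum, the dropout rate, the inflated group size and the total are all stated, so they can be checked against each other. They do not agree. The figure 154 is what results from adding 10% of 140 to 140, whereas a 10% dropout removes 10% of those enrolled. Taken at its own rate, the plan ends below the number that it calls the minimum.

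What is at stake is the accuracy of a planning statement: whether enrolling 308 really protects 140 per group against the loss the protocol expects. Anyone can check this by hand, and a registry entry or publication that copies the sentence would carry the slip forward.

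**Working it through.** **Inputs, all from Section 3 of the protocol.** Stone-free rates 0.85 (RIRS) and 0.95 (PCNL); alpha 0.05; power 0.80; minimum 140 per group; dropout 10%; 154 per group; 308 in total. The protocol does not say whether alpha is one- or two-sided. Two-sided is assumed here, because a one-sided test gives 111 per group (130 with continuity correction), neither of which is close to 140.

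**Step 1: the base figure of 140.** Pooled-variance normal approximation, no continuity correction:

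n = [1.960 × √(2 × 0.90 × 0.10) + 0.842 × √(0.85 × 0.15 + 0.95 × 0.05)]² / 0.10² = 140.1

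This is 141 when rounded up, against the stated 140. Other common formulas give 138 (unpooled variance), 133 (arcsine) and 160 (two-sided with continuity correction). The base figure is reproduced to within one patient and is not in question.

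**Step 2: how 154 arises.** 140 × 1.10 = 154 exactly, and 2 × 154 = 308.

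**Step 3: what 154 leaves after 10% dropout.** 154 × 0.90 = 138.6 per group, against 140. In total, 308 × 0.90 = 277.2 against 280.

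**Step 4: the dropout that 154 does cover.** 1 − 140/154 = 9.1%.

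**Step 5: the enrolment that would keep 140 after 10% dropout.** 140 / (1 − 0.10) = 155.6, so 156 per group and 312 in total, that is 2 more per group and 4 more overall. Check: 156 × 0.90 = 140.4.

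**Step 6: what the shortfall costs in power** (85% versus 95%, two-sided alpha 0.05):

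| Patients per group | Pooled normal | Unpooled normal | Exact power, Pearson chi-square |
|---|---|---|---|
| 138 | 79.4% | 80.2% | 81.6% |
| 138.6 | 79.6% | 80.4% | – |
| 139 | 79.7% | 80.5% | 81.1% |
| 140 | 80.0% | 80.7% | 81.4% |

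Only the pooled approximation, the formula that best reproduces 140, drops below 80%, and then by about 0.4 percentage points at 138.6. The exact power does not rise steadily with n because the outcome counts are discrete; 138 does no worse than 140.

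**The case against.** The best case against raising this is that it changes nothing in practice. Exact power at 138 to 140 per group is above the planned 80% throughout, and the unpooled formula asks for only 138 per group, which 138.6 satisfies. The spread between accepted formulas (133, 138, 141) is wider than the gap between 154 and 156. All of this stands, and it limits the point to a minor correction.

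Three further arguments bear on the arithmetic itself:

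- **The 154 is worded as a floor.** True, but the same sentence gives the total as 308, exactly twice 154. Nothing provides for enrolment beyond that.
- **Multiple imputation may keep patients without a 3-month CT in the analysis.** It may, so the analysed number need not fall to 138. But imputation does not restore the missing outcome information in full, and the sample-size text takes no credit for it. It does not make 154 consistent with 140 after a 10% loss.
- **No formula is shown, and adding 10% of the required number is a common shorthand.** The multiplication by 1.10 is indeed an inference, though from an exact match. However 154 was obtained, 14 losses out of 154 are 9.1%, and the protocol says 10%.

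**Conclusion.** The concern holds. At the protocol's own 10% dropout, 154 per group leaves 138.6, which is 1.4 short of its stated minimum; the figures agree only up to 9.1% dropout. The importance is low: four patients in total, about 0.4 percentage points of power by the pooled normal approximation, and exact power still above 81%. The trial should not be described as underpowered on this account.

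The conclusion rests on reading the dropout rate as a share of the patients enrolled and the minimum of 140 as the number to remain after dropout. The power figures also assume a two-sided test and the protocol's 85% and 95%.

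**What to change.** Reword the sentence in Section 3 and leave enrolment at 308. Either version is accurate:

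- 154 per group (308 in total) allows for about 9% dropout from the minimum of 140; or
- 154 per group (308 in total) leaves about 138 per group after 10% dropout.

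The first is simpler, because it needs no statement about power. If the second is used with a power figure, name the method: 79.4% at 138 per group by the pooled normal approximation, two-sided. An unqualified figure just under 80% would understate the power of the chi-square test.

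The cost is one line of text. Raising the target to 156 per group (312 in total) would also make the figures agree, but the power calculation gives little reason to enrol four more patients.

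### Nothing in the protocol keeps the allocation from whoever reads the 3-month CT, so the 2 mm call that decides the primary outcome may be made knowing the arm

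*Protocol*

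**What the plan says.** Section 3 (Study Design) deals with masking in one line: "Blinding: Open-label". It makes no exception for outcome assessment.

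Section 6 (Outcome Measures) defines the primary outcome: "Stone-Free Rate (SFR) at 3 months: defined as no residual stones or residual fragments <2 mm on non-contrast CT".

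Section 7 (Follow-Up) names CT as the means of looking for residual stones, but names no reader and no reading procedure.

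Section 9 (Safety and Monitoring) covers data checks: "Data will be reviewed by monitors and verified by data managers". These are checks on recorded data, not a masked reading of the scan.

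Section 3 also gives the planning figures used below: "Assuming 85% SFR for RIRS and 95% for PCNL, with alpha=0.05 and power=0.80, the minimum sample size per group is 140".

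**The concern.** The two operations are visibly different, so surgeons and patients can hardly be masked, and describing treatment as open-label is correct. The 3-month CT is another matter. It is read well after surgery, from an image, and open-label treatment does not require that its reader know the arm. Under the protocol as written, a member of the operating team could read the scan and settle the primary outcome, and nothing would have been breached.

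The endpoint is binary with a cut at 2 mm. A clear scan or a large residual stone leaves little room for opinion, but a fragment close to the cut does. If such fragments are resolved differently in the two arms, the comparison is biased, and it can be biased either way. Few failures are expected, so a small number of differential readings could matter.

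This is a matter of trial conduct rather than analysis. A statistical analysis plan, which is not at hand, cannot mask a scan that has already been read unmasked.

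**Working it through.** **Inputs.** From section 3: stone-free rates 85% (RIRS) and 95% (PCNL), alpha 0.05, power 0.80, 140 per group before dropout. Two-sided testing is assumed, because the protocol does not state sidedness. The misreading shares are also assumed, because the protocol does not say how many fragments lie near 2 mm.

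**Step 1: reproduce the plan's figure.** Pooled two-proportion formula, with p̄ the mean of the two rates:

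n = [1.960·√(2p̄(1−p̄)) + 0.842·√(p₁(1−p₁)+p₂(1−p₂))]² / (p₂−p₁)²

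With p̄ = 0.90: [1.960·√0.18 + 0.842·√0.175]² / 0.10² = 140.1, which rounds up to 141. The stated 140 is reproduced to within one patient. A one-sided test would need 111, so the two-sided assumption fits.

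**Step 2: expected failures at 140 per group.**

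- RIRS: 0.15 × 140 = 21
- PCNL: 0.05 × 140 = 7

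**Step 3: rejection rate under assumed misreading in one arm.**

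Power = Φ[(d − 1.960·se₀)/se₁], where d is the apparent difference, se₀ = √(2p̄(1−p̄)/140) and se₁ = √((p₁(1−p₁)+p₂(1−p₂))/140).

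| Scenario | Apparent SFR, RIRS vs PCNL | d | se₀ | se₁ | Rejection rate |
|---|---|---|---|---|---|
| No misreading | 85% vs 95% | 0.10 | 0.0359 | 0.0354 | Φ(0.841) = 80% |
| 2% of RIRS patients wrongly read as stone-free | 87% vs 95% | 0.08 | 0.0342 | 0.0339 | Φ(0.383) = 65% |
| 3% of RIRS patients wrongly read as stone-free | 88% vs 95% | 0.07 | 0.0333 | 0.0331 | Φ(0.141) = 56% |
| 20% of PCNL failures wrongly read as stone-free | 85% vs 96% | 0.11 | 0.0350 | 0.0344 | Φ(1.200) = 88% |

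In patients, the two RIRS rows are 0.02 × 140 = 2.8 and 0.03 × 140 = 4.2, or 13% and 20% of that arm's 21 failures. The PCNL row is 0.20 × 7 = 1.4 patients, or 1% of the arm.

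**Step 4: check the approximation.** Exact binomial enumeration of the uncorrected Pearson test gives 0.814, 0.655, 0.556 and 0.902 for the four rows. The pattern is the same.

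The rows show how sensitive the comparison would be if readings differed by arm. They do not estimate how often that would happen.

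**The case against.** **The point rests on silence.** The open-label statement is true and contradicts nothing, and a reading procedure may sit in an imaging or CRF manual that is not at hand. This stands in part: the documents do not show that the reader will know the arm, only that nothing prevents it. But who determines the primary outcome, and whether masked, is normally stated in the protocol, and this protocol's masking line leaves outcome assessment within open-label.

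**The outcome is fairly objective.** It has a numeric threshold, one modality and one time point. This stands, and it confines the concern to fragments near the threshold.

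**All misreading shares are assumed.** This also stands. Four stronger readings are tempting, and the document supports none of them:

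- *A reader might infer that the trial will be biased, or biased towards RIRS.* The document gives neither the number of borderline fragments nor any sign of which arm a reader would favour.
- *A reader might infer that five scans would overturn the result.* At the expected counts, uncorrected Pearson p moves from 0.0053 (21 vs 7) to 0.0501 (16 vs 7). But this requires five RIRS failures to be reclassified and no PCNL failure. If one or two of the 7 PCNL failures are reclassified as well, p is 0.026 or 0.013. It is a worst case.
- *A reader might count equal misreading in both arms as part of the harm.* If the same 13% or 20% share of failures is misread in each arm, power falls to 73% or 70%. That is ordinary measurement error, which masking does not cure, and it is no part of the case.
- *A reader might infer that the shared stent makes masking secure.* Section 5 does place one in both arms ("A double-J stent is placed postoperatively"; "Double-J stent and nephrostomy tube placed postoperatively"). But it gives no removal time, so nothing shows that a stent is present at 3 months.

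**Masking may fail.** In the PCNL arm the protocol describes "Tract dilation up to F22, nephroscope introduced", and a tract may be visible on CT. The patient's record may also reveal the arm. This stands as a limit on the remedy. Partial masking still removes the most direct route to bias, a reading by the operating team itself.

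**Conclusion.** The point holds as a gap in how the primary outcome is protected. Followed as written, the protocol allows the 2 mm call to be made by someone who knows the arm. It does not say that this will happen, and the size and direction of any resulting bias cannot be derived from it.

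The rejection rates in the table (from 80% down to 65% or 56%, or up to 88%) are illustrations. They rest on the protocol's 85% and 95%, a two-sided 0.05 test, 140 analysed per group and misreading in one arm only. The stated sample size is reproduced and needs no change on this account. This is a cheap improvement worth making, not evidence that the result would be invalid.

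**What to change.** Keep treatment open-label and add one or two sentences to section 3 stating that:

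- the planned 3-month CT is read by someone outside the operating team, through each hospital's existing CT reading where available;
- the allocation is left off the CT request;
- the largest residual fragment is recorded in mm before any discussion with the operating team.

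**Cost.** The added wording, the change to the CT request and one recorded measurement. There is no extra scan, no change to treatment and no change to the sample size. That no staff are added is an assumption: it requires that existing CT reading at each hospital already lies outside the operating team, which the protocol does not say. Where it does not, a reader has to be found.

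**Downside.** Masking will be imperfect, because a percutaneous tract or the patient's record may reveal the arm. It reduces misreading that differs by arm but does not remove it, and it does nothing for error that is equal in both arms.

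### Change in hemoglobin is set for an unadjusted two-group test; ANCOVA on the pre-operative value is, with equal arms and in large samples, never less precise than the t-test on change (optional efficiency gain)

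*Protocol*

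**What the plan says.** Protocol section 6 includes among the secondary outcomes "Change in serum procalcitonin and hemoglobin levels". Section 8 does not match tests to outcomes by name. It has a single rule for all continuous data: "Continuous variables: mean +/- SD, t-test or Mann-Whitney U test as appropriate". The choice left open is between two unadjusted tests. The only model with covariates in that section is "Multivariate logistic regression for outcome prediction", which does not apply to a continuous outcome.

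On design, section 3 plans arms of equal size: "Allowing for 10% dropout, each group will include at least 154 patients; total n=308". Allocation is randomised in blocks. The sample size rests on the stone-free rate alone; no precision or power is stated for hemoglobin.

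**The concern.** Change in hemoglobin cannot be computed without a pre-operative value, so that value will be in the data set. The t-test on change uses it only by subtraction, which amounts to a regression on baseline with the slope fixed at 1. If the true slope differs from 1, part of the between-patient variation that baseline could explain stays in the error term.

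At stake is the width of the interval for one quantitative measure of blood loss in a comparison of a percutaneous with a retrograde operation. Bias and validity are not in question. Infection (SIRS) and complications (Clavien-Dindo) are separate secondary outcomes and are not touched.

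**Working it through.** **The plan's own figure.** The inputs from section 3 are "Assuming 85% SFR for RIRS and 95% for PCNL", alpha 0.05 and power 0.80. The two-sided pooled formula gives

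n = [1.96·√(2·0.90·0.10) + 0.8416·√(0.85·0.15 + 0.95·0.05)]² / 0.10² = (0.8315 + 0.3521)² / 0.01 ≈ 140.1 per group,

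or 141 rounded up. The stated 140 reproduces, and 140 × 1.1 = 154 gives the enrolled number. These figures belong to the primary outcome. The 140 per arm is used below only as a plausible number of evaluable patients.

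**Variance comparison.** Let s0 and s1 be the pre- and post-operative SDs, k = s1/s0, and ρ the pre-post correlation. Per patient, in units of s0²:

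- change score: 1 + k² − 2ρk
- ANCOVA residual: k²(1 − ρ²)
- difference: (1 − ρk)², which is never negative and is zero only when ρk = 1.

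The ratio ANCOVA/change is therefore k²(1 − ρ²)/(1 + k² − 2ρk), and the ratio of interval widths is its square root. With k = 1 the variance ratio simplifies to (1 + ρ)/2.

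**Results.** ρ, k and a pre-operative SD of 15 g/L are assumptions; none is in the protocol. Half-widths are 1.96·√(2/140)·15 = 3.514 g/L times the square root of the relevant variance.

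| k | ρ | change | ANCOVA | ratio | variance saved | CI narrower by | half-width, g/L |
|---|---|---|---|---|---|---|---|
| 1.0 | 0.5 | 1.000 | 0.750 | 0.750 | 25% | 13% | 3.51 → 3.04 |
| 1.0 | 0.7 | 0.600 | 0.510 | 0.850 | 15% | 8% | 2.72 → 2.51 |
| 1.0 | 0.8 | 0.400 | 0.360 | 0.900 | 10% | 5% | 2.22 → 2.11 |
| 1.1 | 0.5 | 1.110 | 0.908 | 0.818 | 18% | 10% | 3.70 → 3.35 |
| 1.1 | 0.7 | 0.670 | 0.617 | 0.921 | 8% | 4% | 2.88 → 2.76 |
| 1.1 | 0.8 | 0.450 | 0.436 | 0.968 | 3% | 2% | 2.36 → 2.32 |
| 1.2 | 0.5 | 1.240 | 1.080 | 0.871 | 13% | 7% | 3.91 → 3.65 |
| 1.2 | 0.7 | 0.760 | 0.734 | 0.966 | 3% | 2% | 3.06 → 3.01 |
| 1.2 | 0.8 | 0.520 | 0.518 | 0.997 | 0.3% | 0.2% | 2.53 → 2.53 |

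Outside this range, with k = 1, the saving is 35% at ρ = 0.3, 5% at ρ = 0.9 and 2.5% at ρ = 0.95.

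**Finite-sample cost.** Estimating the slope inflates the variance by 1 + 1/(280 − 4) = 277/276, about 0.4%. That is the loss when ρk = 1.

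**Simulation (normal data, 140 per arm, 6000 runs).** Empirical variance ratios at ρ = 0.5/0.7/0.8 were 0.75/0.84/0.90 (k = 1), 0.83/0.93/0.97 (k = 1.1) and 0.86/0.97/1.00 (k = 1.2). With post-operative SDs differing between arms (k = 1.0 and 1.3) they were 0.86/0.95/0.99. Coverage of the ANCOVA 95% interval was 94.5–95.4% in all 12 settings. With the effect set so that the t-test on change has about 80% power, ANCOVA reached 90/85/83%, 87/83/81% and 85/82/80% for the three values of k. Mann-Whitney reached 77–78% (2000 runs).

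**Does it need equal arms?** In a further simulation (8000 runs) with slopes of 1.0 and 0.6 in the two arms and 140 per arm, the variance ratio was 0.91. With 70 and 210 patients and slopes of 1.0 and 0.4 it was 1.29. The guarantee therefore depends on equal allocation, which this protocol plans.

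**The case against.** The strongest reply is that nothing here is wrong. The unadjusted test is valid, the protocol sets no precision target for hemoglobin, and baseline adjustment of a secondary outcome is often left to an SAP. Section 8 is a short generic list that does not tie the t-test to hemoglobin and does not expressly exclude a linear model. The benefit rests on assumed values of ρ and k and may be close to nil. The power figures come from an effect chosen to give the t-test about 80%, so they say nothing about this trial's actual power. The guarantee covers the t-test only, although Mann-Whitney is equally allowed.

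Most of this stands and limits the point. The size is assumption-driven, the gain can vanish, and the power figures show relative efficiency only. What does not stand is that the matter is left open. The protocol states a method for all continuous variables, and both options it names are unadjusted. Replacing a stated method with one that is at least as precise as the t-test, from data already collected, is a fair suggestion at low severity.

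Procalcitonin is deliberately outside the claim. Its likely skew is already met by the Mann-Whitney option. In simulations under assumed distributions, log-scale ANCOVA against Mann-Whitney on change ranged from a gain of 9 power points to a loss of 10.

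**Conclusion.** The point holds as an efficiency improvement to consider, not as an error. For change in hemoglobin, ANCOVA on the pre-operative value is in large samples never less precise than the t-test on change, given the equal arms planned. Over the assumed range (ρ 0.5 to 0.8, k 1.0 to 1.2) the variance saving runs from 25% down to 0.3%. With an assumed SD of 15 g/L and 140 per arm, the half-width shrinks by at most about 0.5 g/L (3.51 to 3.04). The worst case, a true slope of 1, costs about 0.4% of variance. No general ordering against Mann-Whitney is claimed, and that hemoglobin falls under the section 8 rule is read from its blanket wording.

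**What to change.** Add to section 8, before comparative data are analysed so that the choice of model cannot follow the results:

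> Post-operative hemoglobin will be compared between groups by ANCOVA with terms for group and pre-operative hemoglobin. The adjusted mean difference will be reported with its 95% CI. The unadjusted test on change will be given as a supporting analysis.

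The question asked is unchanged: with baseline in the model, the group effect is the same whether the outcome is the post-operative value or the change. The cost is wording only. No new data, visits or patients are needed, SPSS fits the model, and one degree of freedom out of about 280 is used. The procalcitonin analysis can stay as it is.

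### The general test rule in section 8 also covers cost and lets a rank test, which does not compare mean cost per patient, decide that outcome (minor)

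*Protocol*

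**What the plan says.** Section 6 of the protocol lists "Cost and stone composition analysis" as the last secondary outcome. Section 8 has one line for continuous outcomes, "Continuous variables: mean +/- SD, t-test or Mann-Whitney U test as appropriate", and one threshold, "p < 0.05 considered statistically significant". It does not say when each of the two tests applies, and nothing takes cost out of the rule. The other entries in section 8 (a test for categorical variables, logistic regression, multiple imputation) do not provide a cost comparison.

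Two further places bear on the shape of the cost data. Section 3 plans on "Assuming 85% SFR for RIRS and 95% for PCNL, with alpha=0.05 and power=0.80, the minimum sample size per group is 140", and section 6 counts "Need for secondary procedures" as an outcome.

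**The concern.** Total spending is the mean cost per patient times the number of patients, so a cost comparison has to rest on arithmetic means. Mann-Whitney asks something else: whether a randomly chosen bill in one arm tends to lie below a randomly chosen bill in the other. A costly minority enters only through its ranks, however large the bills are.

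The two questions give different answers when one arm has a cheaper typical patient but more expensive exceptions, for example a cheaper index stay with more repeat procedures. Costs are usually right-skewed, and skew is the usual reason to choose Mann-Whitney under a rule like this one. The published p-value for cost could then point to a saving, or an excess, that the means do not show.

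**Working it through.** **The plan's own figure.** With stone-free rates of 85% and 95% (average 0.90), two-sided alpha 0.05 and power 0.80, the pooled formula without continuity correction gives

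n = [1.960 × √(2 × 0.90 × 0.10) + 0.842 × √(0.85 × 0.15 + 0.95 × 0.05)]² / 0.10² = (0.8315 + 0.3521)² / 0.01 = 140.1 per group.

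This agrees with the stated 140. The enrolled 154 is 140 × 1.10. I use 140 per arm below.

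**Assumptions, none from the protocol.** Costs are in units of one index PCNL and are log-normal. An index RIRS costs 0.90. A re-treatment costs 1.00 on average. Re-treatment shares are 15% and 5%, borrowed from the planned shares of patients who are not stone-free. Mean costs are then equal:

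- RIRS: 0.90 + 0.15 × 1.00 = 1.05
- PCNL: 1.00 + 0.05 × 1.00 = 1.05

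**What Mann-Whitney sees at CV 15%.** The log-scale SD is √ln(1 + 0.15²) = 0.149. The probability that a RIRS bill is below a PCNL bill is built up as follows:

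- Neither patient re-treated (0.85 × 0.95 = 0.8075): Φ[ln(1/0.90) / (0.149 × √2)] = Φ(0.50) = 0.69, contributing 0.558.
- Only the PCNL patient re-treated (0.85 × 0.05 = 0.0425): close to 1, contributing 0.042.
- Only the RIRS patient re-treated (0.15 × 0.95 = 0.1425): close to 0.
- Both re-treated (0.15 × 0.05 = 0.0075): about 0.63, contributing 0.005.

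The total is about 0.605, although the means are equal. The null standard error is √[281 / (12 × 140²)] = 0.0346, so the expected z is 0.105 / 0.0346 = 3.05. The chance of significance in favour of RIRS is about Φ(3.05 − 1.96) = 0.86.

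**Simulation, equal means** (2,000 to 4,000 trials per scenario, two-sided 0.05). Percentage of trials declaring RIRS cheaper:

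| Cost CV | Mann-Whitney, 15% v 5% re-treated | Mann-Whitney, half of these re-treated, index RIRS 5% cheaper | Welch (first scenario) |
|---|---|---|---|
| 15% | 86 | 43 | 2-3 |
| 20% | 52 | 21 | 2-3 |
| 30% | 17 | 9 | 2-3 |
| 40% | 10 | 5 | 2-3 |
| 50% | 6 | 4 | 2-3 |

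The nominal one-directional rate is 2.5%. Results at 154 per arm are similar.

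**RIRS truly dearer.** With an index RIRS at 0.93, the means are 1.08 and 1.05. Mann-Whitney calls RIRS cheaper in about 40% of trials at CV 15%, 16% at 20%, 4-5% at 30% and 2-2.5% at 50%. Welch does so in under 1%.

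**Where the error disappears or turns round.**

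- Equal index costs, no re-treatment: 2-3% declare RIRS cheaper, the nominal rate.
- Equal index costs, 15% v 5% re-treated (RIRS truly dearer, 1.15 v 1.05): about 0%.
- Plain log-normal costs, equal means, log-SD 0.5 in both arms: 2.2% cheaper, 2.5% dearer. Skew alone does no harm.
- Plain log-normal, equal means, log-SD 0.6 RIRS and 0.3 PCNL: 63% cheaper. With the spreads swapped: 63% dearer.

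**The case against.** The strongest reply is that this is detail for a statistical analysis plan. Section 2 names clinical efficacy and safety as the objective, cost appears once, and section 8 is an outline that allows a t-test and reports means with SDs. A reader would see the mean costs beside any rank-based p-value.

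Part of this stands. The rule permits Mann-Whitney but does not require it, and a conflict with the means could be noticed. Still, the protocol is not silent on cost: its stated rule covers the outcome and admits a test of a different quantity. In simulated data of the kind above, a normality check rejected in every trial, so an analyst who selects by distribution would reach Mann-Whitney.

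A reader might also infer that the trial's own 15% v 5% makes a false finding of cheaper RIRS likely. The documents do not support that:

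- Those figures are shares not stone-free, not re-treatment rates.
- Stone status is read on CT at 3 months, and section 7 describes no later contact, so the cost of any re-treatment prompted by that scan may not be captured.
- The large percentages need an index RIRS 5-10% cheaper and a low CV. In this model the error shrinks towards nominal as costs become more variable.
- The direction depends on which arm has the longer upper tail, which the protocol does not tell us.

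**Conclusion.** The point holds in a limited form and is minor. Section 8, read in the usual way, would have skewed cost judged by a test that does not compare mean cost per patient. The result can mislead in either direction, but only if the arms' cost distributions differ in shape.

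Under the assumed equal-means scenario with 15% v 5% re-treated, the false finding of cheaper RIRS ranges from about 86% of trials at CV 15% to 6% at CV 50%, against 2-3% for Welch. It is absent when index costs are equal. Every cost input is an assumption, so these figures show what the rule allows and do not predict this trial's result. The stone-free-rate comparison and the sample size are not touched.

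**What to change.** Add one sentence to section 8, for example: *Cost per patient is compared as the difference in arithmetic means with a bootstrap or Welch 95% confidence interval; medians and rank tests are descriptive only.*

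This takes a few lines of code and no extra data or patients. The downside is that, with skewed costs, the interval for the mean difference may be wide and the cost result inconclusive.
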